#### **1.2.4.6. Non-melanoma Skin Cancer**

Non-melanoma skin cancers have occurred in patients treated with ibrutinib. Monitor patients for the appearance of non-melanoma skin cancer.

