### **1.3.3. Summary of Clinical Safety**

Up to 1 January 2014, an estimated 2409 patients are available for safety analysis of obinutuzumab in clinical trials. These include patients with CLL or NHL, from doses of 50 mg to 2000 mg in monotherapy or in combination with CHOP, FC, bendamustine, or chlorambucil. To date, the largest and most mature dataset available to assess the safety of obinutuzumab as monotherapy comes from studies BO20999 and BO21003; the largest and most meaningful dataset to assess the safety of obinutuzumab in combination therapy with chlorambucil comes from study BO21004. Overall, most of the safety experience is based on NHL patients currently undergoing treatment with 1000 mg obinutuzumab; however these data currently remain blinded and therefore contribute little to the assessment of the safety profile of obinutuzumab. There is only limited post marketing experience.

The following adverse events are considered as important risks associated or potentially associated with obinutuzumab: Infusion related reactions, tumor lysis syndrome, thrombocytopenia including acute thrombocytopenia, neutropenia, late onset and prolonged neutropenia, prolonged B-cell depletion, infections including Progressive multifocal leukoencephalopathy and hepatitis B reactivation, gastro-intestinal perforation, worsening of pre-existing cardiac conditions, impaired immunization response, immunogenicity, and second malignancies. Most of these are briefly discussed.

The most frequently observed adverse drug reactions (ADRs) in patients receiving obinutuzumab were infusion-related reactions (IRR); these occurred predominantly during the first infusion. The incidence and severity of infusion related symptoms decreased substantially with subsequent infusions, with most patients having no IRRs during the second and subsequent administrations of obinutuzumab. Patients with a high tumor burden (ie, high peripheral lymphocyte count in CLL ( $>25 \times 10^9/L$ ) may be at increased risk of severe IRR. The commonly experienced IRRs are characterized by hypotension, fever, chills, flushing, nausea, vomiting, hypertension, and fatigue, among other symptoms. In the majority of patients, IRRs were mild or moderate and could be managed. Hypersensitivity may be difficult to distinguish from infusion-related reactions; anaphylaxis has been reported in patients treated with obinutuzumab.

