**10.8.1. Adverse Events (AEs)**

Adverse events (AEs) will be graded by the Investigator according to the NCI CTCAE v4.03 for non-hematological AEs. Hematologic toxicity will be assessed by the IWCLL 2008 criteria for grading hematologic toxicity in CLL studies. Verbatim descriptions of AEs will be coded using the current version of the Medical Dictionary for Regulatory Activities (MedDRA). Adverse events that started from the date of the first dose of the first study drug up to 30 days after the date of the last dose of the last study drug, or the first date starting new anticancer therapy, whichever is earliest, are considered treatment-emergent except treatment related AEs. Any treatment related AE will be considered treatment-emergent regardless of the start date of the event. Any event that is present at baseline but worsens in severity or is subsequently considered treatment-related by the investigator will also be considered as treatment-emergent. All-treatment emergent AEs will be summarized by treatment arm. The incidence rates of treatment-emergent AEs will be summarized by System Organ Class (SOC), preferred term, toxicity grade, and relationship to study drug. In addition, SAEs, Grade 3 or above AEs, AEs leading to study treatment discontinuation, delay, reduction, or interruption, AEs leading to death, and events of special interest will be summarized. Multiple occurrence of the same event in a given subject will be counted once at the maximum severity and strongest relationship to study drug.

AEs leading to death and non-fatal SAEs will be listed by subject and tabulated by preferred term.

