#### **11.4.5. Other Malignancies**

All new malignant tumors including solid tumors, skin malignancies and hematologic malignancies will be reported for the duration of study treatment and during any protocol-specified follow-up periods including post-progression follow-up for overall survival. If observed, enter data in the corresponding eCRF.

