5. SAFETY ASSESSMENTS

Safety data will be summarized for the safety population. Table 2 summarizes the safety analyses to be performed.

Adverse events will be coded in accordance with the MedDRA. Severity of AEs will be graded by the investigator according to the NCI-CTCAE v4.03 for non-hematological AEs and IWCLL 2008 guidelines for hematologic toxicity.

Treatment-emergent period is defined as the period from the date of the first dose of study treatment up to 30 days after the date of the last dose of study treatment or the day before initiation of subsequent antineoplastic therapy (including the cross-over ibrutinib monotherapy for arm B subjects), whichever comes first.

The treatment-emergent adverse events (TEAE) are those events that occur or worsen during the treatment-emergent period or that are related to the study treatment. Unless otherwise specified, only TEAEs will be included in the adverse event summaries.

All laboratory values will be converted to and reported as international standard (SI) units. In general, only data from the central laboratory will be summarized and analyzed. Hematologic parameters including platelet counts, hemoglobin, and neutrophils will be assessed by the grading scale for hematologic toxicity in CLL studies in the IWCLL 2008 guidelines. All other gradable laboratory parameters will be graded using the NCI CTCAE v4.03. Unless otherwise specified, only baseline and post-baseline values collected during the treatment-emergent period will be included in the safety analysis.

Table 2: Summary of Safety Assessments

Assessment Type	Definition	Analysis Methods
AE	TEAEs, SAEs, Grade 3 or worse TEAEs, related TEAEs, TEAEs leading to treatment discontinuation, TEAEs leading to dose reduction, TEAEs leading to death, protocol-defined events of special interest and other safety observations. TEAEs within the first 9 months of study treatment and TEAEs in the crossover period	Descriptive summary statistics and/or listings
Lab	Worst post-baseline toxicity grade for selected CTCAE gradable hematology and chemistry. Abnormalities in creatinine clearance, uric acid, and liver function	Descriptive summary statistics and/or listings
Vital Signs and other Observations Related to Safety	Blood pressure, heart rate, new or worsened eye-related symptoms	Descriptive summary statistics and/or listings

TEAE= treatment-emergent adverse event; SAE= serious adverse event; CTCAE= Common Terminology Criteria for Adverse Events.

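### The SAP specifies no analysis of new malignancies over the full period in which they are collected, and its default adverse event window covers far less of Arm B's follow-up than Arm A's

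*SAP*

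**What the plan says.** **Risk.** Protocol 1.3.3 lists, among the important risks associated or potentially associated with obinutuzumab, "impaired immunization response, immunogenicity, and second malignancies". Protocol 1.2.4.6 states: "Non-melanoma skin cancers have occurred in patients treated with ibrutinib".

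**Collection.** Protocol 11.4.5 requires all new malignant tumors to be reported during study treatment and "during any protocol-specified follow-up periods including post-progression follow-up for overall survival". Protocol 3.1 (Follow-up Phase), Protocol 8.3 and the survival row of Appendix A repeat the requirement. Appendix A footnote i adds that new malignancies are reported as adverse events.

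**Analysis.** SAP section 5 sets the default: "Unless otherwise specified, only TEAEs will be included in the adverse event summaries". The treatment-emergent period runs from first dose "up to 30 days after the date of the last dose of study treatment or the day before initiation of subsequent antineoplastic therapy", whichever comes first, and crossover ibrutinib counts as such therapy. TEAEs are "those events that occur or worsen during the treatment-emergent period or that are related to the study treatment"; Protocol 10.8.1 agrees: "Any treatment related AE will be considered treatment-emergent regardless of the start date of the event". SAP Table 2 also lists "protocol-defined events of special interest and other safety observations", TEAEs in the first 9 months of treatment, and TEAEs in the crossover period.

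Neither Protocol 10.8 nor SAP section 5 names an analysis of new malignancies. They are not among the analyses that SAP section 1 defers to separate documents. The only event of special interest that the protocol defines is major hemorrhage (11.4.6.1).

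**The concern.** Second cancers appear slowly, which is presumably why the protocol follows them to the end of survival follow-up. The treatment-emergent window is tied to dosing. Dosing stops after six cycles in Arm B and continues to progression or unacceptable toxicity in Arm A. A table built on that window gives the arms very different time at risk, so equal true incidence would look like an excess on ibrutinib. A late event in Arm B enters the main table only if an investigator in an open-label trial judges it related to treatment that may have ended years before. At stake is whether the long follow-up record on a named risk is used in a way that permits a fair comparison.

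**Working it through.** **Reproducing the design.** The inputs in SAP 1.4 are HR 0.55, 1:1 allocation, 80% power, two-sided 5%, medians of 27 and 49.1 months, 212 subjects at 18 per month, and about 36 months to analysis.

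- Freedman's formula: (1.96 + 0.8416)² × (1.55/0.45)² = 7.849 × 11.864 = 93.1, rounded up to 94, as stated.
- Accrual lasts 212/18 = 11.8 months. Exponential PFS then gives 56.9 (Arm B) + 36.6 (Arm A) = 93.5 events at 36 months, also as stated.

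The design figures can therefore be used to set follow-up time.

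**Arm B window.** The last planned dose is Cycle 6 Day 15, which is day 5 × 28 + 15 = 155. Adding 30 days gives day 185, or 184/30.44 = 6.05 months after first dose.

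**Survival follow-up at 36 months.** Potential follow-up runs from 24.2 to 36 months, mean 30.1. The 36-month OS rates in Protocol 10.7.2.3 (90% in Arm A, 76% in Arm B) give monthly hazards h = −ln(S)/36 of 0.00293 and 0.00762. With accrual time A and analysis time T, mean observed time is 1/h − [e^(−h(T−A)) − e^(−hT)]/(h²A). The results are 28.8 months in Arm A and 26.9 in Arm B.

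**Coverage, Arm B.** The mean window allowing for death is (1 − e^(−0.00762 × 6.05))/0.00762 = 5.9 months. Coverage is 5.9/26.9 = 22%, so 78% lies outside. This assumes that full planned treatment is given; letting progression end it early lowers coverage to about 21%. At 48 months, about 83-84% lies outside.

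**Coverage, Arm A.** The window ends 30 days after the earlier of progression (median 49.1 months) and stopping for another reason, or at death or cut-off if sooner. The documents give no stopping rate, so I assume 0, 1 or 2% per month. Simulated results:

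| Monthly stopping (assumed) | Mean window, months | Share of 28.8 | Ratio to Arm B's 5.9 |
|---|---|---|---|
| 0% | 23.8 | 83% | 4.0 |
| 1% | 21.0 | 73% | 3.6 |
| 2% | 18.7 | 65% | 3.2 |

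With equal arm sizes and the same constant incidence, the last column is also the expected ratio of tabulated malignancies, A to B.

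**First-9-months table.** Capping the windows at 9 months gives 8.5, 8.2 and 7.9 months in Arm A against 5.9 in Arm B, a ratio of about 1.3-1.4.

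**Crossover table.** With no crossover, 78% of Arm B time is uncovered. Suppose instead that every Arm B subject crosses over at progression and all later time counts. About 57% is then uncovered if the 27-month median is read as PFS including death, and about 50% if it is read as time to progression with death separate. The range is about 50-78%, depending on uptake.

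**Sensitivity to constant incidence.** Ignoring deaths and crossover, the rate inside Arm B's window would have to be (30.1 − 6.05)/6.05 = 4.0 times the later rate before half the events fell inside it.

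**Absolute scale.** The documents give no incidence. At an assumed 2% per year, Arm B would have 106 × 0.02 × 26.87/12 = 4.7 malignancies, of which 106 × 0.02 × 5.9/12 = 1.0 falls in the main window. At 1% the figures are 2.4 and 0.5; at 3%, 7.1 and 1.6.

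**The case against.** A reader might infer that most Arm B second malignancies would never be tabulated, or that any conclusion about second cancers would be wrong. The documents do not support either statement.

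- The default opens with an exception clause, and related events are TEAEs at any date. Table 2 has an open category with no stated contents or window. A full-period malignancy table is unspecified, not excluded. Even so, an open category fixes no window, denominator or comparison.
- The crossover-period table would capture malignancies on next-line ibrutinib, related or not. That stands, and it is why the uncovered share is a range. Those events follow ibrutinib exposure, however, so they do not describe the Arm B regimen alone.
- The first-9-months table largely removes the exposure imbalance. That stands for early events; it says nothing about late ones.
- Safety results are descriptive, without tests, and exposure duration is summarized by drug (SAP 3.4), so an alert reader would see the unequal exposure. This softens the risk of misreading but does not supply the missing events.
- Listing SAEs does not fill the gap: under Protocol 11.4.2, SAEs more than 30 days after the last dose are reported only if considered related.
- Collection itself is not perfectly equal. Late visits are every 3 cycles in Arm A from Cycle 36 and every 6 in Arm B from Cycle 39 (Protocol 8.2.1.4). The Appendix I follow-up columns have no malignancy row, although 11.4.5 still requires reporting.

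**Conclusion.** The point holds in this form: the plan collects new malignancies to the end of follow-up and specifies no analysis over that period. By default, events outside the treatment-emergent and crossover windows and not judged related are omitted, mainly in Arm B. At 36 months the main window covers about 22% of Arm B follow-up time and about 65-83% of Arm A's, a ratio of roughly 3 to 4 in expected counts under equal constant incidence. These figures rest on the plan's accrual and survival assumptions, full planned treatment in Arm B, and an assumed 0-2% monthly ibrutinib stopping rate.

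The ratio describes the main TEAE table only. It does not show that the trial would reach a false conclusion: counts would be small under any table, and late related events in Arm B would still enter. This is a cheap improvement and does not affect the validity of the primary analysis.

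**What to change.** Add to SAP section 5 and Table 2 a summary of all new malignancies reported under Protocol 11.4.5, by arm, from first dose to last follow-up. State that it is not limited to the treatment-emergent period. Show non-melanoma skin cancer and all other malignancies separately, with subject counts and rates per 100 person-years. Show Arm B events and person-time after crossover to ibrutinib separately. Cumulative incidence with death as a competing event is optional.

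The cost is one SAP paragraph and one or two tables from data already collected, with no change to treatment or visits. The downside is few events and wide intervals, which the table should show.

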## 8.2. Pre-progressive Disease (Pre-PD) Phase

Following completion of the Screening Visit and once eligibility has been confirmed (per inclusion/exclusion criteria), subjects will be randomized to either Treatment Arm A or Treatment Arm B via an Interactive Web Response System (IWRS) or alternative system provided by the Sponsor. Randomization should occur as close to the time of the expected first dose as possible but no later than 3 days prior to expected first dose with study drug.

For subjects randomized to Treatment Arm A, **ibrutinib** therapy should be continued until disease progression, unacceptable treatment-related toxicity, or other reasons outlined in Section 9.2.

All **other study medications** in both Treatment Arm A and Treatment Arm B should be continued until the protocol specified number of cycles has been completed (or the occurrence of disease progression, unacceptable treatment-related toxicity, or other reasons outlined in Section 9.2 occur first). Each cycle will last for a total duration of 28 days. Local labs may be used to guide all dosing-related decisions and should be followed up with central labs. In the event of clinically suspected disease progression, the subject may continue to receive study medication, at the discretion of the Investigator, until disease progression is confirmed.

All subjects randomized to study treatment will continue following all study procedures and visits following the pre-PD schedule until disease progression is confirmed by IRC, including subjects on Arm B who complete treatment and any subjects who discontinue study treatment early.

Refer to the Schedule of Assessments (Appendix A) for a complete list of procedures to be performed at each scheduled study visit.

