**8.2.1.2. Cycles 2 - 6 Visits**

The following procedures will be performed on Day 1 ( $\pm 3$  days) of each cycle:

- PRO
- Adverse events
- Concomitant medications
- MRU
- Study drug compliance review
- Physical exam

- Vital signs
- ECOG
- CT/MRI scan (Cycle 5 Only)
- Overall response assessment (Cycle 5 Only)
- Hematology
- Serum chemistry (including creatinine clearance)
- Biomarker assays (Cycle 5 Only)
- Flow cytometry blood assays (Cycle 5 Only)
- PK Sampling (subjects in Treatment Arm A only – Cycle 2 Only)

The following procedures will be performed on Day 15:

- Study drug compliance review
- Hematology (may be performed locally)

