#### **8.2.1.3. Cycles 7 - 33 Visits**

For subjects randomized to Treatment Arm A, **ibrutinib** therapy should be continued until disease progression, unacceptable treatment-related toxicity, or other reasons outlined in Section 9.2.

The following procedures will be performed on Day 1 ( $\pm 3$  days) of Cycles 7, 9, 11, 13, 15, 17, 19, 21, 23, 25, 27, 29, 31, and 33:

- PRO
- Adverse events
- Concomitant medications
- MRU
- Study drug compliance review (ibrutinib only)
- Physical exam
- Vital signs
- ECOG
- Hematology
- Serum chemistry (including creatinine clearance) (Cycles 7, 9, 11, and 13, then every 4 cycles)
- CT/MRI Scan (Cycles 9, 13, 17, 21, 25, 29, and 33)

- Bone marrow biopsy/aspirate (Cycle 9 only, unless appropriate for evaluation of PD or CR or to confirm MRD negativity in the peripheral blood)
- Overall response assessment (Cycles 9, 13, 17, 21, 25, 29, and 33)
- Biomarker assays (Cycles 9, 13, 17, 21, 25, 29, and 33)
- Flow cytometry blood assays (Cycles 9, 13, 17, 21, 25, 29, and 33)
- Cytogenetics: FISH panel (Cycle 9 Only)

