## **10. STATISTICAL METHODS AND ANALYSIS**

This section outlines statistical analysis approaches and methods for the study. Specific details for efficacy and safety analyses, including control of multiple testing procedures, will be described in the Statistical Analysis Plan (SAP).

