**10.8.2. Laboratory Evaluations**

All laboratory values will be converted to standard international (SI) units and classified as normal, low, or high based on normal ranges supplied by the central laboratory. Hematologic parameters including platelet count, hemoglobin, and neutrophils will be assessed by the IWCLL 2008 criteria for grading hematologic toxicity in CLL studies. All other gradable laboratory parameters will be graded using the NCI CTCAE v4.03.

Subjects with values outside the normal range will be flagged and summarized by treatment arm. Selected gradable laboratory parameters will be summarized by treatment arm using shift tables. A separate listing and table will be provided to identify and summarize subjects with markedly abnormal changes. In addition, changes from baseline in quantitative parameters will be summarized descriptively by treatment arm at scheduled timepoints.

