#### **11.4.2. Adverse Event Reporting Period**

All AEs whether serious or non-serious, will be documented in the source documents from the time signed and dated ICF is obtained until 30 days following the last dose of study drug. SAEs will be reported to the Sponsor from the time of ICF signing. Both serious and non-serious AEs will be recorded in the eCRF from the first dose of study drug until 30 days after the last dose of study drug.

Serious adverse events reported after 30 days following the last dose of study drug should also be reported if considered related to study drug. Resolution information after 30 days should be provided.

Progressive disease should NOT be reported as an event term, but instead symptoms/clinical signs of disease progression may be reported (see Section 11.1.1).

All adverse events, regardless of seriousness, severity, or presumed relationship to study drug, must be recorded using medical terminology in the source document. All records will need to capture the details of the duration and the severity of each episode, the action taken with respect to the study drug, investigator's evaluation of its relationship to the study drug, and the event outcome. Whenever possible, diagnoses should be given when signs and symptoms are due to a common etiology (eg, cough, runny nose, sneezing, sore throat, and head congestion should be reported as "upper respiratory infection"). Investigators must record in the CRF their opinion concerning the relationship of the adverse event to study therapy. All measures required for adverse event management must be recorded in the source document and reported according to Sponsor instructions.

All deaths should be reported with the primary cause of death as the AE term, as death is typically the outcome of the event, not the event itself. Autopsy and postmortem reports must be forwarded to the Sponsor, or designee, as outlined above, if allowed per local regulatory guidelines.

If a death occurs within 30 days after the last dose of study drug, the death must be reported to the Sponsor as a serious adverse event.

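### For an on-schedule Arm B subject the laboratory safety window closes 44 days after the last obinutuzumab dose, leaving up to 13 of 14 later scheduled blood counts unused although late neutropenia is a named risk

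*SAP*

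**What the plan says.** **The rule.** SAP section 5 states: "Unless otherwise specified, only baseline and post-baseline values collected during the treatment-emergent period will be included in the safety analysis". The period runs from first dose to 30 days after the last dose of study treatment, or to the day before subsequent antineoplastic therapy (including crossover ibrutinib) if that is earlier. The laboratory row of SAP Table 2 specifies nothing different. The nine-month and crossover summaries in that table concern adverse events only.

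**The protocol on laboratory summaries.** Protocol 10.8.2 plans that "changes from baseline in quantitative parameters will be summarized descriptively by treatment arm at scheduled timepoints", with no such cut-off. Protocol section 10, however, leaves the detail to the SAP: "Specific details for efficacy and safety analyses, including control of multiple testing procedures, will be described in the Statistical Analysis Plan".

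**The data collected.** Protocol 8.2 keeps all randomized subjects on the visit schedule until progression is confirmed, "including subjects on Arm B who complete treatment and any subjects who discontinue study treatment early". Protocol 8.2.1.3 lists hematology on Day 1 of "Cycles 7, 9, 11, 13, 15, 17, 19, 21, 23, 25, 27, 29, 31, and 33".

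**The risk.** Protocol 1.3.3 includes "neutropenia, late onset and prolonged neutropenia, prolonged B-cell depletion" among the important risks associated, or potentially associated, with obinutuzumab.

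**Adverse events.** Protocol 11.4.2 says that serious and "non-serious AEs will be recorded in the eCRF from the first dose of study drug until 30 days after the last dose".

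**The concern.** A 30-day window suits an arm treated until progression. It suits Arm B less well, because treatment there stops after six cycles and one of the named risks is late by definition. Neutrophil counts that could describe that risk are scheduled and sent to the central laboratory, and then not used for safety.

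The effect differs by arm. Ibrutinib continues until progression or unacceptable toxicity, so an Arm A subject still on drug contributes every Cycle 7 to 33 count to the tables, including the worst-grade table. An Arm B subject contributes at most one of those 14 counts. The two columns therefore cover unequal observation periods.

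Adverse-event data may not fill the gap. If recording stops 30 days after the last dose, a later non-serious neutropenia in Arm B has no certain place in the adverse-event tables. At stake is a descriptive account of late neutropenia in the control arm, not a hypothesis test.

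**Working it through.** The documents give no day count or visit count for this point, so there is no stated figure to reproduce.

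**Step 1: calendar.** Inputs are 28-day cycles (Protocol 8.2), visits anchored to Cycle 1 Day 1 (Protocol section 8), and Arm B dosing (Protocol 5.2.2). Study day = 28 × (cycle − 1) + day in cycle.

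| Event, Arm B on schedule | Study day |
|---|---|
| Last obinutuzumab, Cycle 6 Day 1 | 28 × 5 + 1 = 141 |
| Last chlorambucil, Cycle 6 Day 15 | 28 × 5 + 15 = 155 |
| Window closes | 155 + 30 = 185 |
| Cycle 7 Day 1 | 169, inside |
| Cycle 9 Day 1 | 225, outside |
| Cycle 33 Day 1 | 897, outside |

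The window closes 185 − 141 = 44 days after the last obinutuzumab dose. Of the 14 visits, 1 is inside and 13 are outside.

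**Step 2: sensitivity to dosing.** A 28-day chlorambucil delay moves the close to day 213, still before day 225, so 13 remain outside. If chlorambucil stops early and Cycle 6 Day 1 obinutuzumab is the last dose, the window closes on day 171. Cycle 7 (day 169 ± 3) is then borderline, and 13 or 14 visits are lost.

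**Step 3: expected counts.** Thirteen is the maximum per subject, because visits stop at progression. Assumptions from the sample-size sections: 212/2 = 106 Arm B subjects, exponential PFS with median 27 months, accrual 212/18 = 11.8 months, cut at 36 months. Follow-up is then uniform on 24.2 to 36 months. No dropout is assumed.

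The expected contribution of a visit at t = (day − 1)/30.44 months is exp(−ln 2 × t/27) × P(follow-up ≥ t). Summed per subject:

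- Cycle 1 Days 8 and 15, and Day 1 of Cycles 2 to 6: 6.64
- Cycle 7 Day 1: 0.87
- Cycles 9 to 33 (outside the window): 7.82
- End-of-Treatment sample at about day 185: 0.86

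Share outside, without the End-of-Treatment sample: 7.82/(6.64 + 0.87 + 7.82) = 7.82/15.33 = 51%, or about 829 of 1,625 counts for 106 subjects. With that sample: 7.82/(15.33 + 0.86) = 48%. Assumed Arm B medians of 20 to 33 months give 48% to 53% without it.

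The Day 15 counts of Cycles 2 to 6 ("Hematology (may be performed locally") add 4.61 per subject. Adding them lowers the share to 7.82/19.93 = 39%, or 38% with the End-of-Treatment sample as well.

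**Step 4: how late the excluded counts are.** Cycle 9 is 225 − 141 = 84 days after the last obinutuzumab dose, Cycle 11 is 140 days after it, and Cycle 33 is 756 days after it. Only Cycles 9 and 11 are within six months: (0.83 + 0.79)/7.82 = 21%. About 57% of the excluded counts are within twelve months.

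**The case against.** **Thirty days is an ordinary choice and the protocol permits it.** This stands. A reader might infer that the SAP contradicts Protocol 10.8.2. It does not: Protocol section 10 hands safety detail to the SAP, and the SAP rule is a default that a further specification can relax.

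**Late neutropenia may still be captured as an adverse event.** This stands in part. Protocol 8.2.1.3 lists adverse events at every Cycle 7 to 33 visit. Protocol 11.4.1 calls for assessment and recording at all evaluation timepoints, and 11.1.1 includes events up to the final study procedures. Related events that are recorded count as treatment-emergent whatever their start date (Protocol 10.8.1, SAP section 5). Against this, Protocol 7.1.1.5 and 11.4.2 end recording at 30 days, after which only related serious events are expressly to be reported. Appendix D also confines hematologic adverse events to clinically significant ones. The text is mixed. A reader might infer that the counts are the only record of late non-serious neutropenia, but the documents support no more than that they are the most systematic one.

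**Other traces exist.** Growth-factor use is collected under medical resource use, although the growth-factor summary in SAP 3.3 stops at the last dose date. Neutrophils also enter the response criteria. Neutropenia that starts in Cycles 1 to 6 is graded inside the window. These records reduce the gap without closing it.

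**The sample total is soft.** This also stands. An assumed dropout of 5% to 10% a year lowers 829 to roughly 772 to 717. Protocol 10.7.2.3 cites 229 randomized subjects rather than 212. The documents also never define when late-onset neutropenia occurs, so the excluded counts cannot all be treated as lost information on that risk.

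**Conclusion.** The point holds as a cheap improvement. For an Arm B subject who completes six cycles on schedule, the window closes on day 185. Up to 13 of the 14 Cycle 7 to 33 hematology visits (those reached before progression) are then left out of the laboratory safety analysis. Roughly half of the expected Arm B post-baseline counts are excluded: 48% or 51%, depending on whether the End-of-Treatment sample is counted. This rests on the design assumptions with no dropout, and on leaving aside the possibly local Day 15 counts.

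Two stronger readings are not supported. The percentages are not missed events; the documents give no rate from which events could be estimated. Nor does the omission flatter ibrutinib. Dropping late Arm B counts can only lower that arm's worst grades or leave them unchanged, which makes the control arm look better if anything. No primary or secondary test is affected.

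**What to change.** Keep the treatment-emergent laboratory table. Add to SAP section 5 and Table 2 one descriptive table of neutrophil grades by arm, using central-laboratory values and the Appendix D scale:

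- Period: first dose to the day before subsequent antineoplastic therapy or progression, whichever is first.
- Split: 30 days after the last obinutuzumab dose.
- Denominator: the number of subjects with at least one count in each interval.
- Footnote: late Arm A counts also reflect ongoing ibrutinib.

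The cost is one SAP paragraph and one extra table from data already collected, with no test and no use of alpha. Its limits should be stated. Counts about 8 weeks apart can miss short episodes, and the table does not isolate an obinutuzumab effect in Arm A.
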